8.5 SAFETY REPORTING CRITERIA TO THE PHARMACEUTICAL COLLABORATORS

Reporting will be per the collaborative agreement.

8.6 REPORTING PREGNANCY

All required pregnancy reports/follow-up to OSRO will be submitted to:

[contact] and to the CCR PI and study coordinator. Forms and instructions

can be found here:

<https://ccrod.cancer.gov/confluence/display/CCRCRO/Forms+and+Instructions>

8.6.1 Maternal Exposure

If a participant becomes pregnant during the course of the study, the study treatment should be discontinued immediately, and the pregnancy reported to the Sponsor no later than 24 hours of when the Investigator becomes aware of it. The Investigator should notify the Sponsor no later than 24 hours of when the outcome of the Pregnancy becomes known.

Pregnancy itself is not regarded as an SAE. However, congenital abnormalities or birth defects and spontaneous miscarriages that meet serious criteria (Section **8.1.2**) should be reported as SAEs.

The outcome of all pregnancies should be followed up and documented.

8.6.2 Paternal Exposure

Male participants should refrain from fathering a child or donating sperm during the study and for two months after the last dose of M7824.

Pregnancy of the participant's partner is not considered to be an AE. The outcome of all pregnancies occurring from the date of the first dose until 2 months after the last dose should, if possible, be followed up and documented. Pregnant partners may be offered the opportunity to participate in an institutional pregnancy registry protocol (e.g., the NIH IRP pregnancy registry study) to provide data about the outcome of the pregnancy for safety reporting purposes.

8.7 REGULATORY REPORTING FOR STUDIES CONDUCTED UNDER CCR-SPONSORED IND

Following notification from the investigator, CCR, the IND sponsor, will report any suspected adverse reaction that is both serious and unexpected. CCR will report an AE as a suspected adverse reaction only if there is evidence to suggest a causal relationship between the study product and the adverse event. CCR will notify FDA and all participating investigators (i.e., all investigators to whom the sponsor is providing drug under its INDs or under any investigator's IND) in an IND safety report of potential serious risks from clinical trials or any other source, as soon as possible, in accordance to 21 CFR Part 312.32.

All serious events will be reported to the FDA at least annually in a summary format.

8.8 SPONSOR PROTOCOL DEVIATION REPORTING

A Protocol Deviation is defined as any non-compliance with the clinical trial Protocol, Manual of Operational Procedures (MOP) and other Sponsor approved study related documents, GCP, or protocol-specific procedural requirements on the part of the participant, the Investigator, or the study site staff inclusive of site personnel performing procedures or providing services in support of the clinical trial.

It is the responsibility of the study Staff to document any protocol deviation identified by the Staff or the site Monitor in the CCR Protocol Deviation Tracking System (PDTs) online application. The entries into the PDTs online application should be timely, complete, and maintained per CCR PDTs user requirements.

In addition, any deviation to the protocol should be documented in the participant's source records and reported to the reviewing IRB per their guidelines. OSRO required protocol deviation

reporting is consistent with E6(R2) GCP: Integrated Addendum to ICH E6(R1): 4.5 Compliance with Protocol; 5.18.3 (a), and 5.20 Noncompliance; and ICH E3 16.2.2 Protocol deviations.

9 CLINICAL MONITORING

Clinical site monitoring is conducted to ensure:

- that the rights of the participants are protected;
- that the study is implemented per the approved protocol, Good Clinical Practice and standard operating procedures; and
- that the quality and integrity of study data and data collection methods are maintained.

Monitoring for this study will be performed by NCI CCR Office of Sponsor and Regulatory Oversight (OSRO) Sponsor and Regulatory Oversight Support (SROS) Services contractor. Clinical site monitoring activities will be based on OSRO standards, FDA Guidance E6(R2) Good Clinical Practice: Integrated Addendum to ICH E6(R1) March 2018, and applicable regulatory requirements.

Details of clinical site monitoring will be documented in a Clinical Monitoring Plan (CMP) developed by OSRO. CMPs will be protocol-specific, risk-based and tailored to address human subject protections and integrity of the study data. OSRO will determine the intensity and frequency of monitoring based on several factors, including study type, phase, risk, complexity, expected enrollment rate, and any unique attributes of the study and the site. The Sponsor will conduct a periodic review of the CMP to confirm the plan's continued appropriateness. A change to the protocol, significant or pervasive non-compliance with GCP, or the protocol may trigger CMP updates.

OSRO SROS Monitoring visits and related activities will be conducted throughout the life cycle of each protocol. The first activity before the study starts is to conduct a Site Assessment Visit (SAV) (as warranted), followed by a Site Initiation Visit (SIV), Interim Monitoring Visit(s) (IMVs), and a study Close-Out Visit (COV).

Some monitoring activities may be performed remotely, while others will take place at the study site(s). Monitoring visit reports will describe visit activities, observations, findings of protocol non-adherence and associated action items or follow-up required for resolution of findings. Monitoring reports will be distributed to the study PI, NCI CCR QA, coordinating center (if applicable) and the OSRO regulatory file.

The site Monitor will inform the study team of any deviations observed during monitoring visits. If unresolved, the Monitor will request that the site Staff enter the deviations in the CCR Protocol Deviation Tracking System (PDTs) for deviation reporting to the Sponsor and as applicable per institutional and IRB guidance.

10 STATISTICAL CONSIDERATIONS

10.1 STATISTICAL HYPOTHESIS

10.1.1 Primary Endpoints

10.1.1.1 Phase I:

The primary endpoint of the phase I portion of the study is to determine the recommended phase II dose (RP2D) of PRGN-2009 (HPV vaccine) alone and in combination with M7824.

10.1.1.2 Phase II:

The primary endpoint of the phase II portion of the study is to determine if HPV vaccine alone (Arm 2A) is able to result in a ≥ 2 -fold increase in CD3+ tumor infiltrating T cells post treatment compared with pre-treatment in participants with p16+ oropharyngeal cancer.

10.1.2 Secondary Endpoints

10.1.2.1 Phase I:

The secondary endpoint of the phase I portion of the study are to determine overall response rate (ORR), progression-free survival time (PFS), overall survival (OS), ratio of participants that are hospitalized because of adverse events attributed to disease progression, and duration of response of the combination therapy in participants with advanced disease.

10.1.2.2 Phase II:

The secondary endpoints of the phase II portion of the study are:

- To determine if the use of HPV vaccine alone results in potentially prolonged survival as compared to the expected 80% three-year historical survival for this population.
- To determine the 3-year overall and relapse-free survival rate for HPV vaccine alone (Arm 2A) in combination with standard of care chemoradiation in participants with p16+ oropharyngeal cancer.

10.1.3 Exploratory Endpoints

The exploratory endpoints of the Phase II portion of the study are:

- To determine if the use of HPV vaccine alone results in potentially prolonged survival as compared to the expected 80% three-year historical survival for this population.
- To determine the 3-year overall and relapse-free survival rate for HPV vaccine alone (Arm 2A) in combination with standard of care chemoradiation in HPV-SNSCC participants.

10.2 SAMPLE SIZE DETERMINATION

The phase I portion of the trial will be conducted using 3+3 dose escalation design evaluating the safety of PRGN-2009 at two dose levels as monotherapy and at the RP2D of PRGN-2009 in combination with a fixed dose of M7824. Using this design up to 22 participants may be enrolled on the phase I portion of the study.

In arm 2A, phase II, 20 participants with p16+ oropharyngeal cancer will be enrolled based on the following reasoning. Assume that a success for any individual participant will be defined as that participant experiencing a two-fold increase in CD3+ tumor infiltrating T cells post treatment compared with pre-treatment. With 20 participants, there would be 80.4% power to detect a difference between 50% and 80% of participants experiencing a success in arm 2A, with an exact binomial test using a one-sided 0.05 significance level. As an illustration, with 20 participants, if 15 participants were able to have a two-fold increase, the lower two-sided 90% confidence bound on 15/20 is 54.4% and the upper two-sided 90% confidence bound is 89.6%. Thus, 15/20 participants would demonstrate the intended magnitude of effect. If 14/20 had this outcome, the lower 90% two-sided bound is 49.2% and the upper two-sided 90% bound is 86.0%, essentially demonstrating nearly the same result.

Expecting that up to 22 evaluable participants will enroll on the phase I portion of the study, that 20 evaluable p16+ oropharyngeal cancer participants will enroll on phase II 2A, and that up to 2 evaluable HPV-SNSCC participants may enroll on phase II 2A, a total of up to 44 evaluable participants will be planned to enroll on this protocol. To allow for a few inevaluable participants the accrual ceiling for this protocol will be set at 50 participants.

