Although positive HPV testing will not be required for the phase I or II portion of the protocol prior to enrolling, HPV testing will be offered as an exploratory endpoint and participants testing negative for HPV after enrolling or whose HPV status cannot be confirmed may be replaced with other participants for the primary efficacy analysis. Participants testing negative for HPV after enrolling or whose HPV status cannot be confirmed may continue to receive treatment on study.

3.1.1 Dose Limiting Toxicity (for first 3-6 participants enrolled on Arms 1A and 1B; phase I part of the study):

Dose-limiting toxicity (DLT) will be defined as any one of the following adverse events, possibly attributable to study drugs, that occur within 28 days of the HPV vaccine monotherapy or 28 days of starting the HPV vaccine + M7824 combination therapy:

- Any Grade 3 or higher bleeding episode requiring blood transfusion(s).
- Any Grade 4 or higher adverse drug reactions (ADRs) as defined by CTCAE v5.0 and assessed as possibly related to any agent by the Investigator, except for laboratory values that are asymptomatic or resolve to Grade ≤ 1 or baseline grade within 7 days without medical intervention.
- Any Grade 3 ADRs possibly attributed to any agent except for any of the following:

- Grade 3 flu-like symptoms or fever, as well as associated symptoms of fatigue, headaches, nausea, emesis which can be controlled with conservative medical management.
- Tumor flare phenomenon defined as local pain, irritation, or rash localized at sites of known or suspected tumor.
- Grade 3 Hgb decrease (< 8.0 g/dL) that is clinically manageable with blood transfusions or erythroid growth factor use does not require treatment discontinuation.
- Grade 3 laboratory values that are asymptomatic or resolve to Grade ≤ 1 or baseline grade within 7 days without medical intervention.
- Keratoacanthoma and squamous cell carcinoma of the skin.
- Any endocrinopathy that can be medically managed with hormone replacement
- Any grade 3 adverse drug reaction which can be medically managed with minimal risk to the participants (e.g., placement of a pleural catheter for recurrent inflammatory pleural effusions) and resolves to at least grade one or baseline grade within 72 hours.

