10.3 POPULATIONS FOR ANALYSES

All participants who receive any investigational treatment will be evaluable for safety and toxicity evaluations.

For phase II, only HPV-OPC participants will be evaluable for primary and secondary objective endpoints. HPV-SNSCC participants will be evaluable only for exploratory objectives.

For phase II, participants who receive at least two doses of therapy and have an adequate pretreatment and posttreatment biopsy will be evaluable for immune infiltration assessments. For phase II, participants who receive at least two doses of immunotherapy and go on to receive standard definitive therapy will be evaluable for relapse free survival and overall survival assessments.

For phase I and II participants, only those participants who have measurable disease present at baseline and have had their disease re-evaluated will be considered evaluable for response. (Note: Participants who exhibit objective disease progression prior to the end of cycle 1 will also be considered evaluable.)

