10.4 STATISTICAL ANALYSES

10.4.1 General Approach

The phase I portion of the study will be conducted as a safety assessment using a 3+3 dose escalation design. In addition, Arm 1B will be expanded to a total of 10 evaluable participants to gauge the preliminary efficacy of the combination of PRGN-2009 and M7824 in participants with advanced disease. The phase II portion of the study will be conducted to evaluate for a potentially significant increase in CD3+ tumor infiltrating lymphocytes with immunotherapy induction.

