10.4.2 Analysis of the Primary Endpoints

Regarding the phase I portion of the study, participants will be evaluated with respect to the grades and types of toxicities obtained. The results will be presented descriptively and tabled if appropriate. Regarding the phase II portion of the study the rate of doubling of baseline CD3+ tumor infiltrating lymphocytes will be provided as well as the 95% confidence interval.

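### Section 10.2 treats 14/20 as nearly equal to 15/20, but 14/20 fails the test that sized arm 2A, and Section 10.4.2 names no test or cut-off to settle it

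*Combined protocol and SAP*

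**What the plan says.** Section 10.2 defines success for a participant as a two-fold rise in CD3+ tumor infiltrating T cells from before to after treatment. On that basis it says "there would be 80.4% power to detect a difference between 50% and 80% of participants experiencing a success in arm 2A" for a sample of 20. The power is attached to a named method: "with an exact binomial test using a one-sided 0.05 significance level".

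It then illustrates with two outcomes. For 15/20 it gives a two-sided 90% interval of 54.4% to 89.6% and concludes that the intended effect would be shown. For 14/20 it says "the lower 90% two-sided bound is 49.2% and the upper two-sided 90% bound is 86.0%, essentially demonstrating nearly the same result".

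The analysis sections are brief. Section 10.4.1 says that phase II will be "conducted to evaluate for a potentially significant increase in CD3+ tumor infiltrating lymphocytes with immunotherapy induction". Section 10.4.2 says that "the rate of doubling of baseline CD3+ tumor infiltrating lymphocytes will be provided as well as the 95% confidence interval". Neither gives a test, a null rate, a success count or a method for the interval.

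**The concern.** The CD3+ doubling rate is the phase II primary endpoint and the only stated basis for the 20 participants. In a single-arm study the conclusion depends on a cut-off fixed in advance. Section 10.2 implies one, then blurs it at the only outcome where it matters: one success short.

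The remark on 14/20 is the only text on how to read that outcome, and it points away from the test in the same paragraph. If 14/20 occurs, the remark supports a positive reading and the sized test a negative one, so the choice could be made after the data are seen.

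**Working it through.** **Inputs** (all from Section 10.2): n = 20; null rate 0.50; alternative rate 0.80; exact binomial test, one-sided 0.05; stated power 80.4%; stated 90% intervals 54.4% to 89.6% for 15/20 and 49.2% to 86.0% for 14/20.

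**Formula.** For the rule of declaring success if X ≥ r, type I error is P(X ≥ r | n, 0.50) and power is P(X ≥ r | n, 0.80), with X binomial.

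**The plan's own figures first.**
- r = 15: type I error = (15504 + 4845 + 1140 + 190 + 20 + 1)/2^20 = 21700/1048576 = 0.0207. Power = 0.8042, which reproduces the stated 80.4%.
- Clopper-Pearson 90% intervals: 15/20 gives 54.4% to 89.6%, and 14/20 gives 49.2% to 86.0%. Both match. The arithmetic in 10.2 is correct.

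**The 14/20 result.**
- r = 14 adds C(20,14) = 38760 to the numerator: 60460/1048576 = 0.0577, above 0.05. This is also the one-sided p-value for 14/20.
- Power with r = 14 is 0.9133.
- So 15 is the smallest count that meets the stated level, and 80.4% is the power of that rule and no other.

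**How likely is exactly 14/20?** P(X = 14) is 3.7% at a true rate of 50%, 12.4% at 60%, 19.2% at 70% and 10.9% at 80%.

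**Does the 95% interval in 10.4.2 settle it?** If it is Clopper-Pearson and is compared with 50%, the lower bounds are 50.9% for 15/20 and 45.7% for 14/20, so at n = 20 it gives the same decision as the test. But 10.4.2 states neither the method nor the comparison. The method matters for the 90% interval that 10.2 uses: Wilson, Jeffreys, Agresti-Coull and Wald put the 14/20 lower bound at 51.5% to 53.1%, above 50%.

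**If the evaluable number is not 20** (conditional). The first three columns after n give the sized test; the last gives the cut-off and power at 80% if an exact 95% interval excluding 50% were the criterion instead.

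| Evaluable n | Test cut-off | Exact type I error | Power at 80% | 95% interval as criterion: cut-off (power) |
|---|---|---|---|---|
| 16 | 12 | 3.84% | 79.8% | 13 (59.8%) |
| 17 | 13 | 2.45% | 75.8% | 13 (75.8%) |
| 18 | 13 | 4.81% | 86.7% | 14 (71.6%) |
| 19 | 14 | 3.18% | 83.7% | 15 (67.3%) |
| 20 | 15 | 2.07% | 80.4% | 15 (80.4%) |
| 21 | 15 | 3.92% | 89.1% | 16 (76.9%) |
| 22 | 16 | 2.62% | 86.7% | 17 (73.3%) |

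A number other than 20 is possible in either direction. Under Section 10.3, only participants who receive at least two doses and "have an adequate pretreatment and posttreatment biopsy will be evaluable for immune infiltration assessments" count. A shortfall is made less likely by Section 10.2 ("To allow for a few inevaluable participants the accrual ceiling for this protocol will be set at 50 participants") and by Section 3.1, under which participants who test HPV-negative or whose status is unconfirmed "may be replaced with other participants for the primary efficacy analysis".

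**The case against.** The best defence is that the rule can be recovered. Section 10.2 names the test, level, rates and sample size, which together fix the cut-off at 15, and only 15/20 is said to show the intended effect. The remark on 14/20 is a hedged illustration with the 49.2% bound printed beside it; it does not say that the null is rejected. As a description of two estimates, 75% and 70% with overlapping intervals, it is defensible. The excess over 5% is 0.77 percentage points (5.77 − 5.00), at one outcome of a small biomarker study with no stated go/no-go decision attached. The probabilities of 10.9% and 19.2% apply where the true rate exceeds 50%, so a positive reading there would not be a false positive.

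Much of this stands. The remark is not an adopted rule, the excess error arises only if someone acts on it, and 10.2 does contain the test. The defence fails on two counts. The remark follows directly on a sentence that reads 15/20 as a conclusion, and it ties 14/20 to that conclusion. And 10.4.2, where the analysis is specified, does not take up the test. The comparison with 5% also understates the change: moving the cut-off from 15 to 14 raises the actual type I error from 2.07% to 5.77%.

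The figures for n other than 20 are secondary, since they need both a different evaluable number and use of the 95% interval as the criterion. Table 8 (Section 14.1.2) lists 22 phase II participants, but that is a safety count that equals the planned 20 oropharyngeal plus 2 sinonasal. It does not show that the biopsy-evaluable number differs from 20.

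**Conclusion.** The concern holds. The numbers in Section 10.2 are right; the reading of 14/20 is wrong for the test that sized the arm, and Section 10.4.2 does not correct it. Accepting 14/20 means a type I error of 5.77% and power of 91.3%, against 2.07% and 80.4% for the rule that was powered. This rests on n = 20 evaluable, a null rate of 50% and the exact test as stated.

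At n = 20 the exact 90% and 95% intervals lead to the same decision, so the confidence level alone does no harm there. It would matter only if the evaluable number were 16, 18, 19, 21 or 22 (within the range 16 to 22) and the 95% interval were used as the criterion. This should be fixed: it bears on the primary conclusion, though at one borderline outcome.

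**What to change.** In Section 10.2, delete the closing remark that equates 14/20 with 15/20 and state that 14/20 does not meet the criterion.

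In Section 10.4.2, state the primary analysis as the one-sided exact binomial test of a doubling rate of at most 50%, at the 0.05 level, with the matching two-sided 90% Clopper-Pearson interval. Keep the 95% interval as descriptive and name its method. List the test cut-offs by evaluable number: 12/16, 13/17, 13/18, 14/19, 15/20, 15/21, 16/22.

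Because Table 8 already lists 22 phase II participants, the amendment should say whether any CD3+ results had been seen when it was written.

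The cost is wording in two sections. No participants or procedures are added, and the rule is the one already powered. The downside is that 14/20 can no longer be presented as positive.

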10.3 POPULATIONS FOR ANALYSES

All participants who receive any investigational treatment will be evaluable for safety and toxicity evaluations.

For phase II, only HPV-OPC participants will be evaluable for primary and secondary objective endpoints. HPV-SNSCC participants will be evaluable only for exploratory objectives.

For phase II, participants who receive at least two doses of therapy and have an adequate pretreatment and posttreatment biopsy will be evaluable for immune infiltration assessments. For phase II, participants who receive at least two doses of immunotherapy and go on to receive standard definitive therapy will be evaluable for relapse free survival and overall survival assessments.

For phase I and II participants, only those participants who have measurable disease present at baseline and have had their disease re-evaluated will be considered evaluable for response. (Note: Participants who exhibit objective disease progression prior to the end of cycle 1 will also be considered evaluable.)

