1.1.2 Secondary Objectives

Phase I in participants with recurrent/metastatic HPV positive cancer:

- To assess overall response rate (ORR) according to RECIST 1.1.
- To assess progression-free survival time (PFS).
- To assess overall survival (OS).
- To assess duration of response.
- To assess ratio of participants that are hospitalized because of adverse events attributed to disease progression.

Phase II in participants with newly diagnosed stage I (T1,2 N1)/II/III p16-positive oropharyngeal cancer (OPSCC) cancer:

- To determine if the use of PRGN-2009 alone results in significantly prolonged survival as compared to the expected 80% three-year historical survival for this population.
- To determine the 3-year overall and relapse-free survival rate for PRGN-2009 alone (Arm 2A) as neoadjuvant/ induction therapy before definitive standard of care therapy for this population.
- To assess the safety of the recommended phase II dose (RP2D) of PRGN-2009 (HPV vaccine) alone in this participant population.

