3.3 DOSE MODIFICATIONS

3.3.1 Discontinuation

Phase 1 and Phase 2:

Treatment with individual agents (PRGN-2009 alone or in combination with M7824) will be discontinued in participants experiencing specific adverse events; subjects will however still remain on study for follow up of survival. Treatment discontinuation will occur in any participant experiencing a DLT-defining toxicity and in the case of:

- Any Grade 4 or higher adverse drug reactions (ADRs) as defined by CTCAE v5.0 and assessed as possibly related to that agent by the Investigator, **except** for any of the following:
 - Laboratory values that are asymptomatic or resolve to Grade ≤ 1 or baseline grade within 7 days without medical intervention.
 - Any endocrinopathy that can be medically managed with hormone replacement.
- Any Grade 3 ADRs possibly attributed to that agent **except** for any of the following:
 - Grade 3 flu-like symptoms or fever, as well as associated symptoms of fatigue, headaches, nausea, emesis which can be controlled with conservative medical management.
 - Tumor flare phenomenon defined as local pain, irritation, or rash localized at sites of known or suspected tumor.
 - Grade 3 Hgb decrease (< 8.0 g/dL) that is clinically manageable with blood transfusions or erythroid growth factor use.
 - Grade 3 laboratory values that are asymptomatic or resolve to Grade ≤ 1 or baseline grade within 7 days with medical management.
 - Keratoacanthoma and squamous cell carcinoma of the skin.
 - Any endocrinopathy that can be medically managed with hormone replacement.
 - Any other grade 3 adverse drug reaction that resolves to grade ≤ 1 or baseline grade within 72 hours.

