6. Participants who have completed neoadjuvant or induction immunotherapy on the phase II portion of the protocol will be followed by phone or email for recurrence, adverse events and survival starting 2 months (+/- 2 weeks) after safety visit and then annually (+/- 1 month) until the patient is 5 years out from surgery or completion of chemoradiotherapy.

7. As indicated in Section **12.3**, all subjects will be offered the opportunity to complete an NIH advanced directive form. This should be done preferably at baseline but can be done at any time during the study as long as the capacity to do so is retained. The completion of the form is strongly recommended but is not required.

8. Biochemical profile: Acute care, hepatic and mineral panel as described in Sections **2.2** and **2.4**.

9. In HIV positive participants.

10. Imaging (CT of neck and chest/ MRI, if indicated, for oropharyngeal cancer participants; CT of skull, neck and chest/ MRI, if indicated, for sinonasal SCC; no CT chest required if PET/CT available) at baseline/screening, and at Week 4-5 (CT of neck/ MRI, if indicated, for oropharyngeal cancer participants; CT of skull, neck/ MRI, if indicated, for sinonasal SCC). MRI (with gadolinium) will be used when CT scan is not an option to follow the disease. Bone scans and other imaging assessments may also be performed as clinically indicated. Post-treatment imaging is to be strongly pursued but is not required and may be waived at the discretion of the PI.

11. Where feasible, biopsies will be done at baseline as well as at week 4-5. Biopsies will be done by ENT under direct visualization. Where feasible at least 2 cores will be obtained. If a recent (\leq 6 months preferred) outside biopsy has been performed that specimen may be used in lieu of a baseline biopsy. For patients that have surgery as definitive treatment, Week 4-5 biopsy may be omitted: in this case tumor biospecimens will be obtained from the institution where the patient underwent surgery after the patient signs that institution's release document.

12. Where feasible, research blood (see Section **5.1**) will be collected at baseline, week 3 and week 45 with the following exceptions:

- Samples for AVA analysis will be taken prior to infusion on W1, W3, with research labs on 4-5 or with end of treatment labs if participants come off treatment prior to any of those timepoints.
- Note: Samples may be sent to Precigen, Inc for additional analyses (see Section **5.1.9**).

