3.6 CRITERIA FOR REMOVAL FROM PROTOCOL THERAPY AND OFF STUDY CRITERIA

Regardless of reason for removal from study therapy, participants will be asked to have a 28 day follow up safety visit. Participants who are unable or unwilling to return for this visit will be asked to review any safety concerns by phone within this time period.

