10.4.4.3 Overall Survival

OS will be evaluated using Kaplan-Meier methods. OS will be defined as the time from the date of first treatment to the date of death (any cause). Subjects who are alive at the end of follow up will be censored at the last known date alive.

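### Phase II overall survival is timed from the first dose but counts only participants who receive two doses and reach definitive therapy, so 3-year OS can be biased, upward if those left out fare worse

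*Combined protocol and SAP*

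**What the plan says.** - **Population.** In section 10.3, phase II participants who get "at least two doses of immunotherapy and go on to receive standard definitive therapy will be evaluable for relapse free survival and overall survival assessments". The same section defines an all-treated set, but only for safety and toxicity.
- **Clock.** Section 10.4.4.3 states: "OS will be defined as the time from the date of first treatment to the date of death (any cause"). The method is Kaplan-Meier and there is no phase II exception. Section 3.2.1 puts the second dose on D15, and definitive therapy follows it, so both entry conditions are met after the clock starts.
- **Use.** Section 1.1.2 asks whether the vaccine alone gives "significantly prolonged survival as compared to the expected 80% three-year historical survival for this population". Section 10.1.2.2 words it as "potentially prolonged survival as compared to the expected 80% three-year historical survival for this population".
- **Follow-up.** Section 3.3.1 says of participants who stop an agent for adverse events that "subjects will however still remain on study for follow up of survival". Section 3.6 adds: "Regardless of reason for removal from study therapy, participants will be asked to have a 28 day follow up safety visit". For the long term, footnote 6 of the phase II calendar (section 3.4.2) says: "Participants who have completed neoadjuvant or induction immunotherapy on the phase II portion of the protocol will be followed by phone or email". This contact runs "until the patient is 5 years out from surgery or completion of chemoradiotherapy".

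**The concern.** The analysis set is chosen by what happens after time zero, but survival is counted from time zero. Everyone kept is certain to have lived until definitive therapy began, and that interval is credited as survival. A treated participant who dies, progresses, withdraws or declines before that point is left out altogether. In a single-arm study read against a fixed 80% rate, the reported figure could exceed the all-treated result without any vaccine effect.

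There is a related gap in follow-up. Footnote 6 describes long-term contact for those who completed induction, and counts its end date from surgery or completion of chemoradiotherapy. For a treated participant who has neither, that end date is undefined. This does not contradict section 3.3.1, but it leaves open how long these people are followed.

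RFS does not share the problem. Section 10.4.4.1 starts its clock at completion of chemoradiation, so it is conditional by definition.

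**Working it through.** **The plan's own figure.** The only phase II design figure is for the primary CD3+ endpoint (section 10.2). With 20 participants, 50% against 80% and a success rule of at least 15/20, the exact binomial power is 0.8042 (stated 80.4%) and the attained one-sided alpha is 0.0207. It reproduces and does not depend on the OS set. No sample size, power or exclusion rate is given for OS.

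**Inputs for OS.** From the documents: the 80% three-year benchmark (1.1.2), 20 oropharyngeal participants (10.2), a usual wait of 4 to 6 weeks for definitive treatment (1.2.9), and an entry criterion against more than 70 days from diagnosis to curative treatment (2.1.2.14). Assumptions: the number excluded k, their 3-year survival p, the time w from first dose to definitive therapy, a true all-treated 3-year OS of 80%, and no censoring before 3 years.

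**(a) Deaths before definitive therapy are the only exclusions.** With constant hazard, λ = −ln(0.80)/156.5 weeks = 0.001426 per week. The reported OS is 0.80/exp(−λw), and the expected early deaths among 20 are 20 × (1 − exp(−λw)).

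| w (weeks) | Reported 3-year OS | Expected early deaths |
|---|---|---|
| 4 | 80.46% | 0.11 |
| 6 | 80.69% | 0.17 |
| 10 | 81.15% | 0.28 |

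The 10-week row is a long case taken from the 70-day criterion. First dose comes after diagnosis, so a participant treated within 70 days of diagnosis has a shorter interval than this.

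**(b) Other treated participants are also excluded.** With 20 treated and 16 alive at 3 years, the reported OS is (16 − kp)/(20 − k). If 20 evaluable participants are reached by replacement (2.3.2.3 counts evaluable participants), 22 are treated, 22 × 0.80 = 17.6 are expected to survive, and with 2 excluded the reported OS is (17.6 − 2p)/20.

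| Survival of the excluded (p) | 1 of 20 excluded | 2 of 20 excluded | 2 of 22 excluded |
|---|---|---|---|
| 100% | 78.9% | 77.8% | 78.0% |
| 80% | 80.0% | 80.0% | 80.0% |
| 50% | 81.6% | 83.3% | 83.0% |
| 0% | 84.2% | 88.9% | 88.0% |

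Case (a) is a special case of (b): k = 0.17 with p = 0 gives 16/19.83 = 80.7%. The two are not added.

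**Context.** The exact 95% interval for 16/20 is 56.3% to 94.3%, so every shift above lies inside sampling error. Table 8 (section 14.1.2) lists 22 phase II participants with no SAE and no grade 4 or 5 event. For 0/22 the exact 95% upper bound is 15.4%. The table does not show how many received two doses or reached definitive therapy.

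**The case against.** The best defence is that the restricted set answers the question asked. Section 10.1.2.2 describes the 3-year rate for vaccine combined with standard chemoradiation, and section 1.1.2 places the vaccine before definitive therapy. The 80% rate may itself describe patients who received definitive treatment. This could justify a conditional population. It does not justify starting that population's clock at the first dose, so the present pairing of set and clock fits neither reading.

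A second argument is that few people will be excluded. Table 8 shows no PRGN-2009-related event of grade 3 or higher among 22 phase II participants, which makes stopping for vaccine toxicity look uncommon. Adverse events are collected to 28 days after the last dose (section 6.1), about day 43 with dosing on D1 and D15, and no grade 5 event is listed. This stands as a reason to expect a small effect. It says nothing about people who decline, progress or withdraw.

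Third, section 3.6.2 lists completion of a 5-year follow-up period as a phase II off-study criterion and does not limit it to people who had definitive therapy. That helps, but the period has no stated start, so the end of contact remains undefined for someone with neither surgery nor chemoradiotherapy.

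Finally, 10 weeks is not a hard cap. Section 2.1.2.14 is an investigator's judgement at entry, and section 3.3.3 contemplates delays of 4 weeks or more beyond the planned start. That is correct, and the 10-week row should be read accordingly.

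**Conclusion.** The concern holds. Followed as written, the plan removes treated participants from OS because of post-baseline events while timing OS from the first dose, and offers no analysis that puts them back.

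The effect is probably small: about 0.5 to 0.7 points if early deaths at 4 to 6 weeks are the only exclusions. With one or two others excluded at 50% survival it is about 1.6 to 3.3 points. The 88.9% figure needs two excluded participants who both die, and is an assumed extreme. If the excluded survive better than those kept, the bias is downward. All of this rests on assumed exclusion numbers, survival and timing.

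The consequence is limited to a secondary comparison with no test or decision rule. The primary CD3+ endpoint, its power and the safety analysis are untouched. The plan should still be changed, because the correction is cheap and the comparison with 80% is a stated objective.

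**What to change.** - **Section 10.3:** make the main phase II OS set all p16+ oropharyngeal participants who receive at least one dose, timed from first dose. Keep the set with two doses plus definitive therapy as supportive.
- **Section 10.4.4.3:** add a line timing the supportive analysis as a landmark from the start of definitive therapy.
- **Reporting:** give the number, reason and vital status of treated participants outside the supportive set.
- **Footnote 6 of section 3.4.2:** extend survival contact to treated participants who do not complete induction or do not receive definitive therapy, in line with section 3.3.1, with an end date at least 3 years from first dose.
- **RFS** can stay conditional.

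The cost is a few sentences in an amendment that needs IRB approval, a second OS estimate, and a few more phone or email contacts. The main OS figure may be slightly less favourable. If the 80% rate applies only to patients who received definitive therapy, the landmark figure is the closer match, which is why both are kept. Participants who withdraw from the study still cannot be followed and would be censored.
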